5.3.1.2.1 Samples for Exploratory Research Variables and Validation Studies

Subjects will have the option to provide samples for exploratory research and validation studies. Subjects may still participate in the main study even if they decide not to participate in this optional exploratory research/validation study.

Exploratory research can help to improve our understanding of how individuals respond to drugs and our ability to predict which subjects would benefit from receiving specific therapies. In addition, exploratory research may help to improve our understanding of how to diagnose and assess/monitor AD by assessing associations between disease characteristics, outcomes data, and biomarkers of interest.

Validation studies, including those related to the development of potential in-vitro diagnostic tests, may be carried out retrospectively in order to assess associations between events of interest (i.e., efficacy and/or safety events) and candidate biomarkers.

For Japan only: research on DNA and RNA exploratory research samples will be restricted to treatment response of pharmacokinetics, efficacy, tolerability, and safety.

AbbVie (or people or companies working with AbbVie) will store the exploratory research/validation studies samples in a secure storage space with adequate measures to protect confidentiality. The samples will be retained while research on ABT-494 (or drugs of this class) or AD and related conditions continues, but for no longer than 20 years after study completion.

All subjects are preferred to have been fasting for a minimum of 8 hours prior to sample collection. If a subject is not able to fast when necessary, due to unforeseen circumstances, the non-fasting status will be recorded in study source documentation. The following samples will be collected according to [Table 3](#) for each subject who consents to provide samples for exploratory research/validation studies:

- DNA samples for pharmacogenetic or epigenetic analyses;
- RNA samples for transcriptomic and/or epigenetic analyses;
- Serum and plasma samples for systemic analyses, including but not limited to proteomic and metabolomics (these samples may be used for assay of study drugs if needed);
- Blood samples for peripheral blood mononuclear cell (PBMC) investigations;
- Skin biopsies for pathological and biological investigations, including, but not limited to transcriptomics, proteomic profiling, immunohistochemistry (IHC), and targeted investigations, e.g., identification of specific analytes, and target identification.

The procedures for obtaining and documenting informed consent are discussed in [Section 9.3](#).

Samples will be shipped to AbbVie or a designated laboratory for RNA/DNA extraction, if applicable, and/or analyses or long-term storage. Instructions for the preparation and shipment of the samples will be provided in the laboratory manual.

Skin Biopsy samples for investigations that include, but are not limited to, epigenetics, transcriptomics, proteomics, IHC and targeted investigations.

For subjects who consent, 2 skin biopsies should be collected at the Baseline and Week 16 visits (one lesional and one non-lesional from the same general area at each visit) and one lesional skin biopsy at the Week 4 visit. Skin biopsies should be between 4.5 and 5 millimeters. Non-lesional skin biopsies should be at least 1.5 centimeters away from the lesional biopsied area and in the same general area. The procedure for obtaining and documenting informed consent is discussed in Section 9.3.

Samples will be shipped to AbbVie or a designated laboratory for extraction, if applicable and/or analyses and/or long-term storage. Instructions for the preparation and shipment of the samples will be provided in a laboratory manual.

Mandatory Exploratory Research/Validation Studies Samples Collection From Selected Sites

Selected sites will be asked to perform a complete investigation of biomarkers. For such sites, these assessments (blood sample and skin biopsy collections) will be made mandatory as part of the main study. There will be a specific ICF for subjects in these selected sites.

5.3.2 Drug Concentration Measurements

5.3.2.1 Collection of Samples for Analysis

Blood samples (plasma) for pharmacokinetic (PK) assay of ABT-494 (upadacitinib) and possibly other medications will be collected as follows:

- At Weeks 2 and 4 prior to dosing;
- At Weeks 8, 12, 16, 20, 24, 32, 40, 52, 64, 76 and 88/PD at any time during the visit.

On Week 2 and Week 4 visit days, if possible, subjects should take the study drug dose at the clinic after collecting the PK blood sample, except if the subjects regularly take the study drug dose at night. Those subjects who regularly take the study drug dose at night should continue to take study drug according to their normal schedule. For all other visits, subjects can take the study drug dose on visit days at their regular schedule and not necessarily at the clinic.

For all PK samples, the date and accurate time of the PK sample collection will be recorded on the lab requisition form. The date and accurate time of the PK sample collection and the last two study drug doses will be recorded on the eCRF to the nearest minute.

Refer to the study specific laboratory manual for detailed instructions on sample collection, processing, and shipment.

5.3.2.2 Measurement Method

Plasma concentrations of ABT-494 (upadacitinib) will be determined by the Drug Analysis Department at AbbVie using a validated liquid chromatography/mass spectrometry method.

5.3.3 Efficacy Variables

5.3.3.1 Primary Variable

The primary endpoint is the mean percent (%) change from Baseline (Day 1) in EASI score at Week 16.

5.3.3.2 Secondary Variables

- Proportion of subjects achieving an EASI 75 response, defined as at least a 75% reduction in EASI score, at Week 16 relative to the Baseline (Day 1)
- Proportion of subjects achieving an Investigator Global Assessment (IGA) of "0" or "1" at Week 16

- Percent change from Baseline to Weeks 2, 8 and 16 in pruritus numerical rating scale (NRS)
- Percent change in EASI score from Baseline at Week 8
- Percent change in SCORAD score from Baseline at Weeks 8 and 16
- Proportion of subjects achieving EASI 50/75/90 response at Weeks 8 and 16
- Proportion of subjects achieving SCORAD 50/75/90 response at Weeks 8 and 16
- Proportion of subjects with Dermatology Life Quality Index (DLQI) = "0" or "1" at Weeks 8 and 16
- Change from Baseline in DLQI at Weeks 8 and 16
- Change and percent change from Week 16 (re-randomization) in EASI score at all Period 2 visits
- Time to loss of EASI 50 response relative to Baseline among those who were re-randomized as EASI 75 responders at Week 16
- Summary of EASI 75 at all visits in Period 2 among those who were re-randomized as EASI 75 non-responders at Week 16

5.3.3.3 Exploratory Variables

- Time to EASI 50/75/90 and IGA "0" or "1" response in Period 1
- Proportion of subjects achieving EASI 50/75/90/100 response at all visits
- Proportion of subjects achieving SCORAD 50/75/90 response at all visits
- Change from Baseline to Week 16 in Patient Oriented Eczema Measure (POEM)
- Change from Baseline to Week 16 in Medical Outcomes Study (MOS) Sleep Scale
- Change from Baseline to Week 16 in Asthma Symptoms Questionnaire
- Change from Baseline to Week 16 in Daytime Nasal Symptoms Questionnaire
- Change from Baseline in total sleep time per night (TST min), Sleep Efficiency (%), Wake After Sleep Onset (WASO), number of scratching

events per hour, mean activity during rest (sleep) periods as measured by actigraphy.

Primary and secondary variables will also be evaluated at all scheduled visits through Week 88.

5.3.4 Safety Variables

Safety evaluations include AE monitoring, physical examinations, vital sign measurements, ECG, and clinical laboratory testing (hematology, chemistry, and urinalysis).

5.3.5 Pharmacokinetic Variables

Plasma ABT-494 (upadacitinib) concentrations will be measured at the times indicated in [Table 2](#). A non-linear mixed-effects modeling approach will be used to estimate the population central values and the empirical Bayesian estimates of the individual values for ABT-494 oral clearance (CL/F) and volume of distribution (V/F). Additional parameters may be estimated if useful in the interpretation of the data.

5.3.6 Exploratory Research Variables and Validation Studies

Optional and mandatory (at selected sites only) samples may be collected to conduct exploratory investigations into known and novel biomarkers. The types of biomarkers to be analyzed may include, but are not limited to nucleic acids, proteins, lipids, or metabolites.

For Japan only: research on DNA and RNA exploratory research samples will be restricted to treatment response of pharmacokinetics, efficacy, tolerability, and safety.

Biomarker assessments may be used to assess and generate prognostic, predictive, pharmacodynamic, or surrogate biomarker signatures. These assessments may be explored in the context of AD or related conditions and/or ABT-494 or drugs of similar

classes. The results from these analyses are exploratory in nature and may not be included with the clinical study report (CSR).

The samples may also be used to develop new therapies, research methods or technologies. In addition, samples from this study may be stored for future use. Samples may then be used to validate putative biomarker signatures obtained from a prospective study, leading to the development of diagnostic tests.

5.4 Removal of Subjects from Therapy or Assessment

5.4.1 Discontinuation of Individual Subjects

A subject may withdraw from the study at any time and for any reason. The Investigator may discontinue any subject's participation for any reason, including an AE, safety concerns, or failure to comply with the protocol. See Section 6.1.7 for toxicity management criteria.

Subjects will be withdrawn from the study immediately if any of the following occur:

- Clinically significant abnormal laboratory results or AEs, which rule out continuation of the study drug, as determined by the Investigator and the AbbVie Therapeutic Area Medical/Scientific Director.
- Serious infections (e.g., sepsis) which cannot be adequately controlled within 2 weeks by anti-infective treatment or would put the subject at risk for continued participation in the trial as determined by the Investigator in consultation with the AbbVie Therapeutic Area Medical/Scientific Director.
- The Investigator believes it is in the best interest of the subject.
- The subject requests withdrawal from the study.
- Inclusion or exclusion criteria violation was noted after the subject started study drug, when continuation of the study drug would place the subject at risk as determined by the AbbVie Therapeutic Area Medical/Scientific Director.
- Introduction of prohibited medications or dosages when continuation of the study drug would place the subject at risk, as determined by the AbbVie Therapeutic Area Medical/Scientific Director.

- Subject is non-compliant with TB prophylaxis (if applicable) or develops active TB at any time during the study.
- The subject becomes pregnant while on study drug.
- Malignancy, except for localized NMSC or carcinoma in-situ of the cervix.
- Subject is significantly non-compliant with study procedures which would put the subject at risk for continued participation in the trial in consultation with the AbbVie Therapeutic Area Medical/Scientific Director.
- Subject develops a gastrointestinal perforation.
- Subjects with disease progression or not responding to treatment are to be withdrawn from the trial based on investigator's discretion.
- In Period 1, discontinuation from study drug will be mandatory for any subject with an EASI score worsening of 25% or more compared with their Baseline EASI score at any 2 consecutive study visits from Week 4 to Week 12.
- In Period 2, discontinuation from study drug will be mandatory for subjects with < EASI 50 response compared with their Baseline EASI score 4 weeks following rescue with topical corticosteroids or at any visit thereafter.

Discontinuation of Study Drug and Continuation of Study Participation

In order to minimize missing data for efficacy and safety assessments, subjects who prematurely discontinue study drug treatment complete a Premature Discontinuation Visit (PD visit) as soon as possible, preferably within 2 weeks. Afterwards, subjects should continue to be followed for all regularly scheduled visits as outlined in [Table 2](#) on standard of care, unless they have decided to discontinue the study participation entirely (withdrawal of informed consent). Subjects should be advised on the continued scientific importance of their data even if they discontinue treatment with study drug early. Subjects that choose to participate in the study after discontinuation of study drug treatment should follow the regular visit schedule as outlined in [Table 2](#); and adhere to all study procedures except for dispensing study drug, PK and exploratory research sample collection. In addition, all future rescue and efficacy-driven discontinuation criteria no longer apply.

Premature Discontinuation of Study (Withdrawal of Informed Consent)

If a subject prematurely discontinues study participation (withdrawal of informed consent), the procedures outlined for the PD Visit should be completed as soon as possible, preferably within 2 weeks of the last dose of study drug, and preferably prior to the initiation of another therapy. In addition, if subject is willing, a 30-day follow-up on-site visit (or phone call if a visit is not possible) after the last dose of study drug may be completed to determine the status of any ongoing AEs/SAEs, the occurrence of any new AEs/SAEs, and medications used to treat AEs/SAEs.

All attempts must be made to determine the date of the last study drug dose and the primary reason for discontinuation of study drug or study participation. The information will be recorded on the appropriate eCRF page. However, these procedures should not interfere with the initiation of any new treatments or therapeutic modalities that the Investigator feels are necessary to treat the subject's condition. Following discontinuation of the study drug, the subject will be treated in accordance with the Investigator's best clinical judgment.

Follow-Up Period

A follow-up visit (or phone call if a visit is not possible) should occur for all subjects approximately 30 days after the last dose of study drug to determine the status of any ongoing AEs/SAEs or the occurrence of any new AEs/SAEs.

For subjects to be considered lost to follow-up, reasonable attempts must be made to obtain information on the final status of the subject. At a minimum, two phone calls must be made and one certified letter must be sent and documented in the subject's source documentation.

Subjects who discontinue the study or study drug prematurely after randomization will not be replaced.

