6.1.7 Toxicity Management

The toxicity management of the AEs including AEs of special interest consists of safety monitoring (review of AEs on an ongoing basis, and periodical/ad hoc review of safety issues by a safety data monitoring committee), interruption of study drug dosing with appropriate clinical management if applicable, and discontinuation of the subjects from the study drug. The management of specific AEs and laboratory parameters is described below.

For subjects who discontinued study drug but continued study participation and are on standard of care therapies, these toxicity management requirements do not apply (including alerts from the central lab) and any intolerability to standard of care therapies should be managed by the prescribing physician.

Serious Infections: Subjects should be closely monitored for the development of signs and symptoms of infection during and after treatment with study drug. Study drug should be interrupted if a subject develops a serious infection or an opportunistic infection. A subject who develops a new infection during treatment with study drug should undergo prompt diagnostic testing appropriate for an immunocompromised subject. As appropriate, antimicrobial therapy should be initiated, and the subject should be closely monitored. Re-challenge with study drug may occur once the infection has been successfully treated. If study drug has been interrupted for more than 14 consecutive days in Period 1 or more than 21 consecutive days in Period 2, the subject must be

discontinued from the study drug. Subjects who develop active TB must be discontinued from the study drug.

Serious Gastrointestinal Events: Subjects presenting with the onset of signs or symptoms of a serious gastrointestinal event should be evaluated promptly for early identification of gastrointestinal perforation. If the diagnosis of gastrointestinal perforation is confirmed, the subject must be discontinued from the study drug.

Cardiovascular Events (MACE): Subjects presenting with potential cardiovascular events should be carefully monitored. These events will be reviewed and adjudicated by an independent Cardiovascular Adjudication Committee in a blinded manner.

Malignancy: Subjects who develop malignancy other than NMSC or carcinoma in-situ of the cervix must be discontinued from the study drug. Information including histopathological results should be queried for the confirmation of the diagnosis.

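### Protocol 5.4.1 orders withdrawal from the study for reasons that its own EASI items, section 6.1.7 and the retention rule treat as stopping study drug only

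*Protocol*

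**What the plan says.** Protocol 5.4.1 puts 14 items under one opening line: "Subjects will be withdrawn from the study immediately if any of the following occur". The last two items, the Period 1 EASI-worsening rule and the Period 2 rule after topical corticosteroid rescue, each call only for mandatory discontinuation of study drug. The non-response item goes the other way: "Subjects with disease progression or not responding to treatment are to be withdrawn from the trial based on investigator's discretion".

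Protocol 6.1.7, to which 5.4.1 refers, covers three of the listed events and stops study drug only:
- Malignancy: "Subjects who develop malignancy other than NMSC or carcinoma in-situ of the cervix must be discontinued from the study drug".
- Gastrointestinal perforation: "If the diagnosis of gastrointestinal perforation is confirmed, the subject must be discontinued from the study drug".
- Tuberculosis: "Subjects who develop active TB must be discontinued from the study drug".

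Section 6.1.7 also has a paragraph for subjects who are off study drug but still in the study on standard of care.

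The retention rule is in the protocol Synopsis, section 5.1, section 5.4.1 directly after the list, and SAP 4.2. Subjects who stop study drug early go on attending the regular visits, in order to limit missing efficacy and safety data. The one exception given is withdrawal of informed consent.

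**The concern.** A site with a subject who develops, say, a malignancy cannot satisfy both rules. If it ends participation, it breaks the retention rule. If it keeps the subject in follow-up, the case fits the deviation category in protocol 7.0 and SAP 7.4 for subjects who met withdrawal criteria and stayed in.

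The statistical stake is avoidable missing data. In Period 1, a subject taken out of the study before the Week 16 window loses an EASI value that the plan meant to collect off drug. The primary analysis (protocol 8.1.5.1, SAP 10.3) would then fill that value by LOCF. In Period 2, later scheduled visits would be lost.

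**Working it through.** The plan gives no figure on this point, so the check is mainly a comparison of texts. The 14 items of 5.4.1 fall into these groups:

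| Items in 5.4.1 | Number | What other text says | Conflict with the opening line |
|---|---|---|---|
| Period 1 EASI worsening; Period 2 EASI after topical rescue | 2 | The items themselves stop study drug only | Direct |
| Malignancy; GI perforation; active TB | 3 | 6.1.7 stops study drug only | Direct |
| AE/laboratory findings; eligibility violation; prohibited medication | 3 | The trigger is that study drug cannot safely continue; no separate consequence is stated | Through the retention rule |
| Progression or non-response | 1 | The item itself says withdrawal from the trial | Through the retention rule |
| Uncontrolled serious infection | 1 | 6.1.7 interrupts drug, then stops it past a time limit | Consequence differs; triggers are not comparable |
| Best interest; procedural non-compliance | 2 | No counterpart in 6.1.7 | None that is clear |
| Subject's request; pregnancy | 2 | Other text agrees that participation ends | None |

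Count: 2 + 3 + 3 + 1 + 1 + 2 + 2 = 14. Five items conflict directly (2 + 3) and four more through the retention rule (3 + 1). In the TB item, the part on non-compliance with prophylaxis has no counterpart in 6.1.7; only the active-TB part is contradicted there.

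What one withdrawal costs:
- **Period 1.** SAP Table 2 sets the Week 16 EASI window at Days 100 to 126. With 40 subjects planned per arm (protocol 8.2), one subject withdrawn with no EASI from Day 100 on removes 1/40 = 2.5% of the planned Week 16 values in that arm. A premature-discontinuation visit inside the window can still supply the value.
- **Period 2.** A withdrawal at Week 20 removes up to seven later scheduled visits: Weeks 24, 32, 40, 52, 64, 76 and 88.

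These are counts per subject, not effects on an estimate. The documents give no expected number of such withdrawals, so no effect on bias or power follows.

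**The case against.** The strongest reply is that the retention instruction stands directly after the list and is repeated elsewhere, so a careful site would follow it. It is also true that an order to stop study drug does not by itself forbid leaving the study. But 6.1.7 provides for subjects who stop drug and stay, and the retention rule says that they are followed. The opening line of 5.4.1 is the text that does not fit.

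Several stronger readings are tempting, and the documents do not support them.

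- **That nearly every item is wrong.** The AE/laboratory, eligibility and prohibited-medication items mention study drug in the trigger, not in the consequence. They conflict with the retention rule, not with their own wording.
- **That pregnancy has two rules.** Table 2 notes n and o, the ineligibility statement in 5.3.1.1, and 6.1.6 together support leaving the study. Permanent stopping of drug, also in 5.3.1.1, is compatible with that.
- **That the infection limits clash.** Section 5.4.1 speaks of "Serious infections (e.g., sepsis) which cannot be adequately controlled within 2 weeks by anti-infective treatment", which is about control of the infection. Section 6.1.7 says "If study drug has been interrupted for more than 14 consecutive days in Period 1 or more than 21 consecutive days in Period 2", which is about the length of a dosing gap. A clash on Days 15 to 21 of Period 2 appears only if both clocks are assumed to start together.
- **That investigators should lose the power to end participation.** Section 5.4.1 grants it: "The Investigator may discontinue any subject's participation for any reason, including an AE, safety concerns, or failure to comply with the protocol". Where participation itself is the risk, as in the procedural non-compliance item, leaving the study is coherent.

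The reply is also right that the consequences are limited:
- The 30-day follow-up remains, and adverse events are followed to resolution (protocol 5.4.1, 6.1).
- Treatment-emergent event summaries and laboratory analyses stop 30 days after the last dose (SAP 11.2.1, 11.3), so later off-drug visits add little to them.
- The Period 2 EASI item applies only after topical rescue, when efficacy data are already imputed or excluded (protocol 8.1.5, SAP 10.1.5).
- LOCF keeps any subject with a post-baseline EASI in the primary analysis.

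**Conclusion.** The inconsistency is real, stands in the current text, and should be corrected. It is direct for five items and runs through the retention rule for four more.

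The harm is probably small and cannot be computed. It depends on how many sites follow the opening line rather than the retention paragraph, and on how many subjects have such an event before Day 100. A reader might infer that the primary result is materially biased; nothing in the documents shows that.

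Two further points bear on the size. Protocol 8.1.5 imputes Period 1 EASI-worsening stops by LOCF in any case, so for them the primary analysis would change little. SAP 10.1.5 does not repeat that rule, however, and on its text retained off-drug values would be used, so losing them could matter somewhat more. SAP Appendix B 10.5 suggests, by inference, that Period 1 was well advanced by the SAP date. A correction then would mainly protect Period 2 visits, which are summarised descriptively (protocol 8.1, SAP 10.1).

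**What to change.** 1. Reword the opening line of the 5.4.1 list so that the listed events lead to immediate discontinuation of study drug, and state that scheduled visits continue under the retention paragraph. Apply it to ten items: AE/laboratory findings, uncontrolled serious infection, eligibility violation, prohibited medication, TB, malignancy, GI perforation, progression or non-response, and both EASI criteria.
2. In the non-response item, replace withdrawal from the trial with discontinuation of study drug.
3. Put the other four items in a short separate list of reasons that end participation: the subject's request, pregnancy, and best interest and procedural non-compliance where the investigator judges that continued participation itself, not only study drug, puts the subject at risk.
4. Make the deviation category in protocol 7.0 and SAP 7.4 match the two lists.

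Leave unchanged the two-week serious-infection criterion and the investigator's power to end participation on safety grounds. Changing either would be a substantive decision that this inconsistency does not require.

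The cost is protocol wording, one category label in the SAP, and the ethics approval that an amendment needs (protocol 9.1). No procedures are added, because the off-drug visits are already scheduled.
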